6.1.2. Analysis Methods

The adverse events will be summarized by intervention arm and by analysis phase. Adverse events will be allocated to phases based on their start date. If the start date of an event falls between (or on) the start and stop date of a study phase, the AE will be attributed to that phase (treatment-emergent principle). For imputation of partially/fully missing dates please see Section 2.5.1. In

case of a completely missing start date, the event is allocated to the double-blind study intervention phase, except if the end date of the AE falls before the first administration of study treatment (DB Day 1).

An overview table will summarize the incidence of TEAEs classified in the following categories: AEs, serious AEs, related AEs, AEs leading to treatment discontinuation, COVID-19 AEs (serious and non-serious) and fatal AEs by presenting by intervention arm the number and percentage of participants who experienced at least one of such AE. The overview AEs table will be also presented stratified by the subgroup of interests identified in Section 2.4.2.

AE relationship to study treatment is grouped into either related or not related category. A related AE is defined as with possible, probable, or very likely relationship with study treatment; not related, otherwise.

All adverse events will be presented in a descending order by incidence based on all participants (Total column). The following TEAEs tables will be included in the analysis:

- All TEAEs
- Serious TEAEs
- At least grade 3 TEAEs
- At least grade 2 TEAEs and related
- TEAEs leading to treatment discontinuation
- Related TEAEs

All serious TEAE, related TEAE, TEAE leading to death, TEAE leading to discontinuation, TEAE of at least grade 3, or AESIs will be listed separately. Listings will include all information collected on the Adverse Event CRF pages (e.g. information on time of onset, duration of events, time of resolution, concomitant therapies and relationship to study treatment).

For participants reporting rash, a listing with specific grade will be provided and Rash questionnaire will be tabulated by study intervention arm and overall.

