6.1.3. Adverse Events of Special Interest

Incidence of treatment-emergent adverse events of special interest will be summarized by intervention arm and analysis phase. The adverse events of special interest include:

- ALT/AST elevations
- Injection Site Reactions
- Renal complications
- Hematologic abnormalities (platelet count, hemoglobin, reticulocytes, neutrophil count)
- Cholesterol increase

The list of all preferred terms belonging to ALT/AST elevations, renal complications, cholesterol increase, and hematologic abnormalities is provided in 0. Injection site reactions will be identified using the eCRF Injection Site Reaction form.

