attachment 2: Adverse events of special interest list of preferred terms.

Adverse Event of Special Interest	Source	Preferred Term
ALT/AST elevation	(Modified) Liver related investigations, signs and symptoms (SMQ) narrow, (as per MedDRA version used for the analysis)	Alanine aminotransferase abnormal Alanine aminotransferase increased Aspartate aminotransferase abnormal Aspartate aminotransferase increased Hepatic enzyme abnormal Hepatic enzyme increased Hepatic function abnormal Hypertransaminasaemia Liver function test abnormal Liver function test increased Transaminases abnormal Transaminases increased
Renal Complications	(Modified) Acute renal failure (SMQ) broad (as per MedDRA version used for the analysis)	Acute kidney injury Anuria Nephropathy toxic Oliguria Renal failure Renal impairment Subacute kidney injury Blood creatinine abnormal Blood creatinine increased Creatinine renal clearance abnormal Creatinine renal clearance decreased Creatinine urine abnormal Creatinine urine decreased Crystal nephropathy Glomerular filtration rate abnormal Glomerular filtration rate decreased Nephritis Proteinuria Renal function test abnormal Renal tubular disorder Renal tubular dysfunction Renal tubular injury Renal tubular necrosis

Adverse Event of Special Interest	Source	Preferred Term
		Urine output decreased Nephropathy Nephropathy toxic Glomerulonephropathy Nephrolithiasis
Cholesterol increase	Dyslipidaemia (SMQ), (as per MedDRA version used for the analysis)	Blood cholesterol abnormal Blood cholesterol esterase increased Blood cholesterol increased Dyslipidaemia High density lipoprotein abnormal High density lipoprotein decreased High density lipoprotein increased Hypercholesterolaemia Hyperlipidaemia Hypo HDL cholesterolaemia Intermediate density lipoprotein decreased Intermediate density lipoprotein increased LDL/HDL ratio decreased LDL/HDL ratio increased Lipid metabolism disorder Lipids abnormal Lipids increased Lipoprotein abnormal Lipoprotein increased Low density lipoprotein abnormal Low density lipoprotein decreased Low density lipoprotein increased Non-high-density lipoprotein cholesterol decreased Non-high-density lipoprotein cholesterol increased Primary hypercholesterolaemia Remnant hyperlipidaemia Remnant-like lipoprotein particles increased Total cholesterol/HDL ratio abnormal Total cholesterol/HDL ratio decreased Total cholesterol/HDL ratio increased Very low density lipoprotein abnormal

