Adverse Event of Special Interest	Source	Preferred Term
		Very low density lipoprotein decreased Very low density lipoprotein increased
Hematologic abnormalities	(Modified) Haematopoietic cytopenias affecting more than one type of blood cell (SMQ), (as per MedDRA version used for the analysis)	Aplastic anaemia Autoimmune aplastic anaemia Bicytopenia Bone marrow failure Cytopenia Febrile bone marrow aplasia Full blood count decreased Gelatinous transformation of the bone marrow Immune-mediated pancytopenia Pancytopenia Panmyelopathy Aspiration bone marrow abnormal Biopsy bone marrow abnormal Blood count abnormal Blood disorder Bone marrow disorder Bone marrow infiltration Bone marrow myelogram abnormal Bone marrow necrosis Bone marrow toxicity Haematotoxicity Myelodysplastic syndrome Myelodysplastic syndrome transformation Myelofibrosis Myeloid metaplasia Plasmablast count decreased Scan bone marrow abnormal
Hematologic abnormalities	(Modified) Haematopoietic erythropenia (SMQ), (as per MedDRA version used for the analysis)	Aplasia pure red cell Aplastic anaemia Erythroblast count decreased Erythroid maturation arrest

Adverse Event of Special Interest	Source	Preferred Term
		Erythropenia Hypoplastic anaemia Microcytic anaemia Proerythroblast count decreased Red blood cell count decreased Reticulocyte count decreased Reticulocytopenia Anaemia Erythroblast count abnormal Erythropoiesis abnormal Haematocrit abnormal Haematocrit decreased Haemoglobin abnormal Haemoglobin decreased Leukoerythroblastic anaemia Normochromic anaemia Normochromic normocytic anaemia Normocytic anaemia Proerythroblast count abnormal Red blood cell count abnormal Reticulocyte count abnormal Reticulocyte percentage decreased
Hematologic abnormalities	(Modified) Haematopoietic leukopenia (SMQ), (as per MedDRA version used for the analysis)	Agranulocytosis Band neutrophil count decreased Band neutrophil percentage decreased Basophil count decreased Basophilopenia B-lymphocyte count decreased Cyclic neutropenia Eosinopenia Eosinophil count decreased Febrile neutropenia Granulocyte count decreased Granulocytes maturation arrest Granulocytopenia Idiopathic neutropenia Leukopenia Lymphocyte count decreased

Adverse Event of Special Interest	Source	Preferred Term
		Lymphopenia
		Metamyelocyte count decreased
		Monoblast count decreased
		Monocyte count decreased
		Monocytopenia
		Myeloblast count decreased
		Myelocyte count decreased
		Neutropenia
		Neutropenic infection
		Neutropenic sepsis

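### The Cholesterol increase AESI counts every term of a dyslipidaemia list, including four falls in non-HDL lipids that contradict the label and four other falls it does not describe

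*SAP*

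**What the plan says.** Section 6.1.3 lists five AESIs, one of them *Cholesterol increase*. Injection site reactions are identified from their own eCRF form. For the other four the SAP states: "The list of all preferred terms belonging to ALT/AST elevations, renal complications, cholesterol increase, and hematologic abnormalities is provided in 0". The cross-reference is broken, but the list meant is plainly Attachment 2, which carries that title. On reporting, the same section says: "Incidence of treatment-emergent adverse events of special interest will be summarized by intervention arm and analysis phase".

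In Attachment 2 the source for this category is "Dyslipidaemia (SMQ), (as per MedDRA version used for the analysis"). Several parameters appear in both directions:

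- "Low density lipoprotein decreased Low density lipoprotein increased Non-high-density lipoprotein cholesterol decreased"
- "Intermediate density lipoprotein decreased Intermediate density lipoprotein increased LDL/HDL ratio decreased LDL/HDL ratio increased"
- "Total cholesterol/HDL ratio abnormal Total cholesterol/HDL ratio decreased Total cholesterol/HDL ratio increased"
- "Very low density lipoprotein decreased Very low density lipoprotein increased"

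Section 6.1.2 adds a listing: "TEAE of at least grade 3, or AESIs will be listed separately".

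**The concern.** The label states a direction and the list does not keep to it. Section 6.1.3 says which terms belong to the AESI, so Attachment 2 is its working definition, and a programmer will flag any adverse event whose preferred term is on the list. A participant whose only lipid event is an LDL decrease is then counted under *Cholesterol increase*.

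The other lists suggest this was not intended. Attachment 2 has seven source rows (one each for ALT/AST, renal and cholesterol, four for hematologic abnormalities). Six are marked as modified; the cholesterol row alone is not. The ALT/AST elevation list, whose label also states a direction, contains no decrease term. Decrease terms do appear in the renal and hematologic lists, but there they fit the label, as with a reduced filtration rate or platelet count.

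At stake is whether a by-arm safety table can report a fall as a rise.

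**Working it through.** The SAP states no count, so there is no figure to reproduce. The check is a direct count of the cholesterol row in Attachment 2, classified by the wording of each term.

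| Group | Terms | n | Share of 33 |
|---|---|---|---|
| Falls in non-HDL lipids | LDL, VLDL, IDL, non-HDL cholesterol decreased | 4 | 12.1% |
| Ratio decreases | LDL/HDL; total cholesterol/HDL | 2 | 6.1% |
| Low HDL | HDL decreased; Hypo HDL cholesterolaemia | 2 | 6.1% |
| No direction | seven 'abnormal' terms (blood cholesterol, HDL, lipids, lipoprotein, LDL, total cholesterol/HDL ratio, VLDL); Dyslipidaemia; Lipid metabolism disorder | 9 | 27.3% |
| Upward wording | all remaining terms | 16 | 48.5% |

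Sum: 4 + 2 + 2 + 9 + 16 = 33. Terms describing a fall: 4 + 2 + 2 = 8.

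**The falls are not all alike.** The four non-HDL falls are the opposite of the label. A ratio to HDL can fall because HDL rises, so the two ratio decreases are not necessarily its opposite, but they are not cholesterol increases. The two low-HDL terms are adverse changes that the label does not describe.

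**The upward terms are mixed too.** The 16 include HDL increased, blood cholesterol esterase increased and two ratio increases (a ratio can rise because HDL falls). Setting these aside leaves 16 − 4 = 12.

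**Comparison list.** ALT/AST elevation has 12 terms: five 'increased' plus Hypertransaminasaemia, giving 6 upward; 6 'abnormal'; 0 decreases.

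**Search for a direction filter.** Sections 6.1.1 to 6.1.3 and Attachment 2 contain none. Section 6.2.1 derives worst toxicity by direction, but for laboratory values, not coded adverse events.

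**Exposure.** Table 6 lists total, HDL and LDL cholesterol and triglycerides. It does not list IDL, VLDL, non-HDL cholesterol or either ratio. Of the four non-HDL falls and two ratio decreases, only LDL decreased names a listed parameter.

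**Scale, as illustration only.** Section 1.2 gives 52 participants and 4:1 allocation. Assume the realised split follows the ratio and everyone is treated: 52 × 4/5 = 41.6, about 42, and 52 × 1/5 = 10.4, about 10. In the double-blind phase, one participant counted solely through a wrong-direction term would move an arm's percentage by 1/42 = 2.4 points or 1/10 = 10 points. How often such events are coded is unknown.

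**Size of the list after deletion.** Removing the four non-HDL falls and two ratio decreases: 33 − 6 = 27. Moving the two low-HDL terms: 27 − 2 = 25, that is 16 upward + 9 without direction.

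**The case against.** The strongest reply is that nothing is hidden. Attachment 2 names the Dyslipidaemia SMQ as the source and prints every term, so *Cholesterol increase* can be read as a short name for a grouping adopted whole. Whether to prune such a grouping is partly a matter of preference. This stands in part: it makes the label the plainest defect and favours renaming over deleting. It does not make the count right under the present label.

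A second reply is that little depends on it. Section 6 makes all safety summaries descriptive with no inferential comparison, AESIs are listed individually, laboratory toxicity is split by direction (6.2.1) with low/normal/high shift tables (6.2.2), and no decision in the SAP uses this rate. Table 6 further narrows the route by which most of these events would arise, although derived or local values could still be reported. All of this stands, and it sets the weight of the point.

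A third reply is that deletion does not give a pure list. That is also correct: the 25-term list would still hold HDL increased, the esterase term, two ratio increases and nine terms without direction.

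**Conclusion.** The point holds as a small mismatch between label and definition. Eight of 33 terms describe a fall. Four would be counted as the opposite of what the label says, and the other four under a label that does not describe them. The effect is limited to the descriptive AESI incidence table and the AESI listing. This rests on reading Attachment 2 as the operative definition, which Section 6.1.3 supports, and on finding no direction rule for coded events.

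A reader might infer three stronger things that the SAP does not support:

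- That all eight falls contradict the label. Only the four non-HDL level falls clearly do.
- That the other terms are cholesterol increases. Nine have no direction, and at least four of the 16 upward terms are not plain cholesterol increases.
- That the reported AESI rate is biased by some amount or between arms. The frequency of such codes is unknown, and the one-participant illustration gives sensitivity, not an estimate.

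**What to change.** **Main fix, before lock.** Rename the AESI to dyslipidaemia / lipid abnormalities in Section 6.1.3 and Attachment 2, keeping all 33 terms. Report cholesterol or atherogenic-lipid increases on their own line, separate from decreases, low HDL and terms with no direction. State where HDL increased, cholesterol esterase increased and the two ratio increases go; that is a medical choice, but it should be written down.

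**Acceptable alternative.** Keep the label, delete the four non-HDL level decreases and the two ratio decreases, move the two low-HDL terms to their own line named in Section 6.1.3, and mark the source as modified. The nine terms without direction can stay, as the ALT/AST list keeps its six, with their direction checked in the AESI listing. Events coded to the deleted terms remain in the general TEAE tables.

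**Cost.** Either is a text edit to one list and to Section 6.1.3, with matching table programming and no new data. The SAP does not show whether the database is locked. If it is, a corrected table label or a footnote giving the direction of the counted terms would serve.
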